6.2. Exclusion Criteria

Patients will be excluded from study enrollment if they meet any of the following criteria within the screening period, which is CCI [Redacted] to the start of study drug, unless otherwise specified below:

For rescreening activities within the screening period, see Section 6.4.

Gastrointestinal Exclusion Criteria

[13] Have a current diagnosis of CD, IBD-Unclassified (formerly known as indeterminate colitis), ulcerative proctitis (distal disease limited to the rectum), or primary sclerosing cholangitis.

[14] Have a documented history of CCI [redacted]

[15] Previous bowel resection or intestinal or intra-abdominal surgery:

CCI [redacted]

- Have had any small bowel or colonic surgery within CCI [redacted] prior to baseline.
- Have had any non-intestinal intra-abdominal surgery within CCI [redacted] of baseline.

[16] Have evidence of toxic megacolon, CCI [redacted] the small bowel or colon.

[17] Have any history or current evidence of cancer of the gastrointestinal tract.

CCI [redacted]

Criteria for Discontinuing Prohibited Medications

[19] Have received any of the following for treatment of UC within the timeframes specified below:

[19a] Corticosteroid enemas, corticosteroid suppositories, or IV corticosteroids CCI [redacted] prior to screening endoscopy.

[19b] 5-ASA enemas or 5-ASA suppositories CCI [redacted] prior to screening endoscopy.

[19c] CCI [redacted]

CCI [Redacted]

[19d] Anti-TNF antibodies (for example, infliximab, adalimumab, or golimumab) within CCI [Redacted] prior to screening endoscopy.

[19e] CCI [Redacted]

[19f] [Redacted]

[19g] Any investigational therapy (biologic or non-biologic) within CCI [Redacted] prior to the screening endoscopy or within 5 half-lives prior to the screening endoscopy, whichever is longer.

[19h] CCI [Redacted]

[19i] CCI [Redacted]

[20] Have failed anti-IL12p40 antibodies (for example, ustekinumab [STELARA®]) or have ever received anti-IL-23p19 antibodies (for example, risankizumab [BI-655066/ABBV-006], brazikumab [MEDI-2070], guselkumab [CNTO1959], or tildrakizumab [MK-3222]) for any indication, including investigational use.

Infectious Disease Exclusion Criteria

[21] Patients who:

[21a] Have evidence of active TB, or

[21b] Have a past history of active TB, regardless of treatment, or

[21c] Have a past history of latent tuberculosis infection (LTBI) and have not completed an appropriate TB treatment regimen (Section 9.4.5.2) or

[21d] Are diagnosed with LTBI at screening.

CCI [Redacted]

[22] CCI

[23] Have human immunodeficiency virus (HIV)/acquired immunodeficiency syndrome (AIDS), test positive for HIV antibodies at screening (see Section 6.2.1).

[24] Have acute or chronic hepatitis B infection or test positive for hepatitis B virus (HBV) at screening, defined as:

[24a] Positive for hepatitis B surface antigen (HBsAg+).

OR

[24b] Positive for anti-hepatitis B core antibody (anti-HBc+) and positive confirmatory PCR for HBV deoxyribonucleic acid (DNA) (see Section 9.4.5.4).

OR

[24c] Detectable HBV DNA (see Section 9.4.5.4).

[25] Have current hepatitis C infection, or test positive for hepatitis C virus (HCV) at screening, defined as:

- Positive for hepatitis C antibody and detectable HCV ribonucleic acid (RNA) (see Section 9.4.5.5).

CCI

[26] Had *Clostridium difficile* or other intestinal infection within CCI of screening endoscopy, or test positive at screening for *C. difficile* or for other intestinal pathogens. CCI

[27] Have a current or recent acute, active nonserious extraintestinal infection for which signs and/or symptoms are present or treatment, if indicated, is not yet complete CCI prior to screening.

[28] Patients with serious, opportunistic or chronic/recurring extraintestinal infections should be adequately treated and off antibiotics for CCI without recurrence of symptoms prior to screening. Serious extraintestinal infections include but are not limited to the following:

[28a] Infections requiring IV antibiotics.

[28b] Infections requiring hospitalization.

[28c] Infections that are considered “opportunistic” (examples are listed in [Appendix 9](#)).

[28d] Chronic, recurrent infections (for example, osteomyelitis and recurring cellulitis).

Patients with an opportunistic infection or chronic, recurrent infection [CCI] [REDACTED] should be discussed on a case-by-case basis with the medical monitor.

[29] Have evidence of active/infectious herpes zoster infection or primary varicella zoster infection [CCI] [REDACTED] prior to screening. Infections are considered active until all vesicles are crusted over.

General Exclusion Criteria

[30] Have had lymphoma, leukemia, or any malignancy within [CCI] [REDACTED] of screening.

Exceptions: The following conditions are not exclusionary:

- a) Basal cell or squamous epithelial carcinoma of the skin that has been adequately treated with no evidence of metastatic disease for at least [CCI] [REDACTED]
- b) Cervical carcinoma in situ that has been adequately treated with no evidence of recurrence within [CCI] [REDACTED] of baseline.

[31] Are investigator site personnel directly affiliated with this study and/or their immediate families. Immediate family is defined as a spouse, parent, child, or sibling, whether biological or legally adopted.

[32] Are Eli Lilly and Company (Lilly) employees or employees of third-party organizations involved with the study.

[33] Are currently enrolled in any other clinical study involving an investigational product or any other type of medical research judged not to be scientifically or medically compatible with this study.

[34] Have previously completed or withdrawn from this study or any other study investigating mirikizumab after receiving study drug. This criterion does not apply to patients undergoing rescreening procedures.

[35] Have had extra-abdominal surgery and have not recovered fully following surgery, including complete wound healing, before screening.

[36] Have presence of significant uncontrolled neuropsychiatric disorder or judged at risk of suicide in the opinion of the investigator;

OR

For patients [CCI] [REDACTED] [REDACTED] during the screening period prior to dosing at Visit 2;

OR

CCI [REDACTED]

AND

CCI [REDACTED]

- [37] Have an unstable or uncontrolled illness, including but not limited to a cardiovascular, respiratory, gastrointestinal (excluding UC), neurological or neuropsychiatric disorders, that would potentially affect patient safety within the study or confound efficacy assessment.
- [38] Have a known hypersensitivity to any component of mirikizumab or monoclonal antibodies.
- [39] Have a solid organ transplant or hematopoietic stem cell transplantation.
- [40] Are unwilling or unable to comply with the use of a data collection device to directly record data from the subject.
- [41] Are unsuitable for inclusion in the study in the opinion of the investigator or sponsor for any reason that may compromise the subject's safety or confound data interpretation.
- [42] Are pregnant, lactating, or planning pregnancy (both males and females) while enrolled in the study or within CCI [REDACTED] after receiving the last dose of study drug.
- [43] Have current or history of alcohol dependence and/or illicit drug abuse within the last year.
- [44] Have abnormal 12-lead electrocardiogram (ECG) that, in the opinion of the investigator or sponsor, increases the risks associated with participating in the study.
- [45] Use marijuana (both recreational and medicinal uses including cannabidiol [CBD] oil). Marijuana use must be stopped prior to screening and is prohibited for the duration of the study.
- [46] Had a blood transfusion in the last CCI [REDACTED] prior to hematology blood sample collection.

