6.4. Screen Failures

Allowed rescreening of patients after initial screen failure

Patients who have failed screening because of the following Inclusion/Exclusion Criteria may be rescreened when the reason for screen failure has resolved:

- [5]
- [6]
- [7]
- [8]
- [9]
- [11]
- [12]
- [15]
- [18c] (once polyps have been removed)
- [19]
- [22]
- [27] to [30]
- [35]
- [42]
- [45], and
- [46].

Individuals may be rescreened up to 2 times, for a maximum total of 3 screens unless additional rescreening is approved via sponsor's medical monitor or designee.

Participants who have failed screening because of Exclusion Criterion [21c] CCI may be rescreened 1 time (see Section 9.4.5.2).

Participants who have failed screening because of Exclusion Criterion [26] may be rescreened 1 time for *C. difficile* stool toxin. Additionally, a participant may be rescreened 1 time for stool culture or ova parasite. In either situation, participant rescreening should only occur after the reason for screen failure has resolved. It is recommended that the investigator confirms the participant has a negative *C. difficile* stool toxin/stool culture/stool ova parasite (as applicable) before performing additional rescreening investigations (see also Section 9.4.5.7). The interval between rescreening visits should be at CCI unless a shorter interval has been agreed with the study's medical monitor. Each time rescreening is performed the participant, parent/guardian must sign a new informed consent form (ICF) and will be assigned a new identification number.

Participants who screen fail because they are unable to complete their endoscopy prior to Visit 2 will not be required to undergo repeat TB testing, chest X-ray (CXR) or computed tomography (CT), HIV, HBV, and HCV testing stool cultures, and *C. difficile* testing if these were normal or negative during screening after discussion with sponsor medical monitor or designee. These tests should be repeated if based on the investigator's judgment the patient has risk factors and/or signs and symptoms of illness. Participants may undergo repeat rescreening sooner than CCI between screen failure and rescreening.

Disallowed rescreening of patients after initial screen failure

Patients who have failed screening because of the following Exclusion Criteria may **not** be rescreened:

- [10]
- [13]
- [14]
- [16]
- [18a] and [18b]
- [20]
- [21a] and [21b] (if current or past history of active TB)
- [23] to [25]
- [31] to [34]

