9.4.5.2. Tuberculosis Testing

Initial Screening

All patients will be screened for active TB and LTBI. Screening for LTBI (Visit 0) will include the following:

- Thorough medical and social history to determine risk factors for TB infection over lifetime, symptoms or signs of active TB, and physical examination, including body temperature measurement and assessment of peripheral lymph nodes, as described in Section 9.4.5.1.
- Two tests to assess immune response to mycobacterial antigens (unless patient has a history of a positive IGRA):
 - IGRA (for example, QuantiFERON-TB Gold or T-SPOT.TB), and
 - Tuberculin skin test (TST, also called a purified protein derivative [PPD] or Mantoux test).
- CXR, as described in Section 9.4.5.3.

This testing paradigm follows the recommendation from NASPGHAN for pediatric patients with IBD starting on anti-TNF therapy (Ardura et al. 2016).

Tests for Immune Response to Mycobacterial Antigens

Patients with documentation of a “negative” IGRA or TST within CCI before initial screening may not need to repeat TB testing at screening, based on judgment of the investigator. Source documentation must include the original laboratory report (for IGRA) or a record of the size in millimeters of the induration response (for TST). A TST recorded as “negative” without documenting the size of induration in millimeters will not be acceptable and will require a retest.

Interpretation of Screening Tests for LTBI

The QuantiFERON-TB Gold assay will be reported as negative, indeterminate, or positive. The T-SPOT assay will be reported as negative, borderline, or positive.

The TST should be read 48 to 72 hours after test application. Skin induration CCI in diameter is interpreted as positive in patients without a BCG vaccination history. In patients with a prior BCG vaccination history, a positive result shall be defined using local criteria recommendation/guidelines. Any questions should be referred to the medical monitor.

Patients with a diagnosis of LTBI based on a positive IGRA test result or a positive TST response, and no evidence of active TB on medical history, physical examination, and CXR, may be evaluated as described in Retesting and Confirmatory testing or rescreened once, as indicated in Section 6.4.

Patients may be enrolled in the study if they are treated for LTBI and meet the following requirements:

- No history of risk of re-exposure since their treatments were completed

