- Have received at least CCI of appropriate ongoing prophylactic therapy for LTBI, based on national or international guidelines, for example, United States Centers for

Disease Control and Prevention (CDC 2016); or the World Health Organization (WHO 2018), with documentation of having completed the appropriate TB prophylaxis regimen,

- No evidence of reactivation of LTBI, and
- Have no evidence of hepatotoxicity (ALT and AST levels must remain $\leq 2 \times \text{AAULN}$) upon retesting of serum ALT and AST levels before treatment assignment).

Such patients must meet all other inclusion and exclusion criteria for participation, and also must continue and complete appropriate LTBI therapy during the course of the study to remain eligible to participate.

Retesting and Confirmatory Testing

One retest is allowed for patients with an “indeterminate” QuantiFERON-TB Gold assay or “borderline” T-SPOT assay. Patients with 2 indeterminate QuantiFERON-TB Gold assays or 2 borderline T-SPOT assays will be required to have a CXR (see Section 9.4.5.3). If both the CXR and TST are negative and there are no other risk factors for TB exposure present, the patient is eligible to be enrolled in the study.

Confirmatory testing with an IGRA is allowed for selected patients who have a positive TST, positive QuantiFERON-TB Gold assay or positive T-SPOT assay who meet all of the following criteria, and are assessed by the investigator as likely having a false-positive test result:

- No risk factors for LTBI
- No risk factors for increased likelihood of progressing from LTBI to active TB, and
- Have never resided in a high-burden country, as detailed in [Appendix 8](#).

If the confirmatory test is positive, the patient will be excluded from the study unless they complete at least CCI of appropriate therapy for LTBI based on national or international guidelines (as defined above), and have no evidence of hepatotoxicity CCI upon retesting of serum CCI of LTBI treatment. Such patients must continue and complete appropriate full course of LTBI therapy during the course of the study to remain eligible to participate in the study. If the confirmatory test is negative, these results will be discussed with the medical monitor in order to determine eligibility for the study.

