Patients with a negative TST or IGRA can be re-tested with an IGRA where, in the judgement of the investigator, the initial test result may be a false negative, for example, due to a technical difficulty in administering the TST or due to concomitant immunosuppressant therapy.

Monitoring for TB During the Study

For all patients, monitoring for TB is to be continuous throughout the study. At a minimum, each participant is to have the following documented at least every CCI

CCI

If the patient has a risk factor ([Appendix 8](#)), the investigator should collect [CCI], as described in Section [9.4.5.3](#)

Diagnosis of LTBI During Study

Patients diagnosed with LTBI during the study [CCI] [redacted]. If treatment for LTBI is considered to be appropriate, the patient must complete [CCI] of appropriate therapy for LTBI, based on national or international guidelines (as defined above), and have no evidence of hepatotoxicity [CCI] of [redacted] upon retesting of serum ALT and AST levels after at least [CCI] of LTBI treatment. Such patients may then resume study drug and must continue with and complete a full course of treatment for LTBI in order to continue on study drug. Non-compliance with LTBI treatment during the study is a reason for permanent discontinuation from study drug (Section [8.1.1](#)).

Household Contact

Throughout the study, patients who have had household contact with a person with active TB must be evaluated for TB infection.

Prior Treatment for LTBI

Patients who have a documented history of completing an appropriate TB prophylaxis regimen with no history of risk of re-exposure since their treatments were completed and no evidence of active TB are eligible to participate in the study. These patients should not undergo TST or IGRA testing unless advised to do so based on local guidelines.

Active TB

Patients with a past history of active TB, without documented treatment by WHO and/or CDC criteria are excluded from the study (Section [6.2](#)).

Patients diagnosed with active TB at screening will be excluded (Section [6.2](#)) and should be referred by the investigator for appropriate TB treatment and follow-up.

If a patient is diagnosed with active TB during the study, the study drug will be permanently discontinued (Section [8.1.1](#)), and the patient will undergo an ETV and then enter the post-treatment follow-up period. The patient should also be referred by the investigator for appropriate TB treatment and follow-up.

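### Protocol 9.4.5.2 restates the past-active-TB exclusion more narrowly than criterion [21b], and its conditions for enrolling treated latent TB cannot all be met together.

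*Protocol*

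**What the plan says.** **Past active TB.** Section 6.2 excludes a patient who meets any listed criterion. Criterion [21b] covers patients who "Have a past history of active TB, regardless of treatment, or". Section 6.4 places [21a] and [21b] on the list for which rescreening is not allowed and makes no exception for treatment. Section 9.4.5.2, under Active TB, points to Section 6.2 and says: "Patients with a past history of active TB, without documented treatment by WHO and/or CDC criteria are excluded from the study".

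**Latent TB infection (LTBI).** Criterion [21c] excludes patients who "Have a past history of latent tuberculosis infection (LTBI) and have not completed an appropriate TB treatment regimen", with a reference to 9.4.5.2. In that section, under Interpretation of Screening Tests for LTBI, a list opens with "Patients may be enrolled in the study if they are treated for LTBI and meet the following requirements". Its first condition refers to re-exposure since treatment ended. Its second asks for a minimum period (length redacted) of prophylaxis that it calls ongoing, and in the same bullet "with documentation of having completed the appropriate TB prophylaxis regimen". The paragraph after the list says that these patients must meet all other entry criteria and "must continue and complete appropriate LTBI therapy during the course of the study to remain eligible to participate".

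Two other parts of 9.4.5.2 describe routes to entry:
- Prior Treatment for LTBI makes patients with a documented completed regimen eligible, given no risk of re-exposure and no active TB.
- Retesting and Confirmatory Testing lets a patient with a positive confirmatory test enter after a minimum period of therapy (length redacted), with the full course finished on study.

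**The concern.** Each rule should give a site one answer for one child. For past active TB, one text makes treatment history irrelevant. The other makes it part of the test while naming the first as its source. If every past case is excluded, the qualifier about documented treatment does no work, so a reader of 9.4.5.2 will look for a reason why it is there. For LTBI, the same patients are described as still on therapy, as having finished it, and as due to finish it later.

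This is an infection-safety criterion for an immunomodulating antibody in children, and an error in either direction has a cost. Under Section 8.1.3, a child enrolled against the criteria should come off study drug unless the sponsor documents approval to continue. A child wrongly turned away is lost to a small study: Section 10.1 plans about 30 enrolled to obtain at least 25 evaluable for pharmacokinetics, a margin of about 30 − 25 = 5.

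**Working it through.** No arithmetic bears on the conflict itself. The check is to set the texts side by side and apply each one to the patients it could cover.

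**(a) Past active TB**

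| Patient | 6.2 [21b] | 6.4 | 9.4.5.2, Active TB |
|---|---|---|---|
| Past active TB, no documented treatment | Excluded | No rescreening | Excluded |
| Past active TB, documented treatment | Excluded | No rescreening | Not mentioned |

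The first row agrees everywhere. In the second row, 6.2 and 6.4 give an answer and 9.4.5.2 is silent, although it presents itself as a restatement of 6.2. The group that 9.4.5.2 excludes is a subset of the group that [21b] excludes. A site applying both texts excludes both patients. A site applying 9.4.5.2 alone has no text there that excludes the second patient. Neither sentence is redacted.

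**(b) LTBI enrolment conditions in 9.4.5.2**

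| Requirement | Child who finished the regimen before entry | Child still on therapy at entry |
|---|---|---|
| No re-exposure risk since treatment was completed | Can be met | Presupposes a completion that has not happened |
| Minimum period of therapy, described as ongoing | Therapy is no longer ongoing | Can be met |
| Documentation that the regimen is complete | Can be met | Cannot be met |
| Continue and complete therapy during the study | Nothing left to continue | Can be met |

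Neither column satisfies every row, and on the question of completion there is no third kind of patient. The list and the paragraph after it therefore cannot be followed as written.

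The likely source shows when the rows are matched to the two routes described elsewhere in 9.4.5.2. The completion rows match Prior Treatment for LTBI and agree with [21c]. The ongoing and continue-and-complete rows match the route after a positive confirmatory test. The list appears to combine the two without saying which condition belongs to which route.

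**The case against.** The strongest reply on active TB is that the two sentences are not opposites. Section 9.4.5.2 never calls treated past active TB eligible. Under Prior Treatment for LTBI, the paragraph just before it, the protocol states eligibility outright when it means it. Any single criterion in 6.2 is enough to exclude, and Section 6 permits no waivers, so 9.4.5.2 cannot relax [21b]. This stands. A reader might infer from 9.4.5.2 that treated patients may enrol, but the documents do not say so, and a site applying every criterion in 6.2 would exclude them. What remains is a restatement narrower than its source, with the risk confined to a site that works from the TB section alone.

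On LTBI, the reply is that the two routes are each intelligible elsewhere in 9.4.5.2, so the confusion is limited to one list. That is fair as to its extent. It does not rescue the list, which also governs enrolment. One could try to read the completion clause as meaning completion of the minimum period only. But the clause speaks of the whole regimen, and the first condition also treats therapy as finished.

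A reader might go further and set criterion [21d] ("Are diagnosed with LTBI at screening") against the enrolment route in 9.4.5.2. The documents do not support that. Text next to [21d], and text after the mention of [21c] in 6.4, is redacted and may hold the linking exception. For the same reason it cannot be shown that every child part-way through LTBI treatment is classified differently by different sections.

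**Conclusion.** Two inconsistencies stand on unredacted current text. First, 9.4.5.2 restates the past-active-TB exclusion more narrowly than [21b], which it cites, and than the rescreening bar in 6.4 implies. Second, the LTBI enrolment conditions in 9.4.5.2 cannot all be met by any patient.

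The size is modest. The documents give neither the country mix nor the frequency of past TB or LTBI, so the number affected is unknown and may be small. No sample size, endpoint or analysis changes. The point deserves correction because it concerns who may be enrolled on an infection-safety criterion and because the correction is simple.

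The conclusion assumes that the redacted durations are only durations and do not change the words around them. It makes no claim about [21d] and takes no view on which rule is clinically right.

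**What to change.** Reconcile Sections 6.2 [21b] and [21c], 6.4 and 9.4.5.2:

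1. State one rule for past active TB in 6.2, and have 6.4 and the Active TB paragraph of 9.4.5.2 refer to it or repeat it in the same terms.
2. In 9.4.5.2, separate the LTBI enrolment conditions by route. For each route, say whether therapy must be complete or may still be under way at entry, and what must be documented. Align [21c] and its rescreening provision in 6.4 with that statement.

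Which rule applies in each case is for the sponsor's clinical team. The cost is wording in a protocol amendment or a clarification letter to sites. The SAP needs no change.
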